Rationnel et Objectifs	
Le cytochrome P450 2C19 (CYP2C19) est l'enzyme responsable du métabolisme de médicaments fréquemment prescrits en clinique comme l'oméprazole, un antiacide inhibiteur de la pompe à proton (IPP), le citalopram, un antidépresseur inhibiteur sélectif de la recapture de la sérotonine (ISRS) ou le clopidogrel, un antiagrégant plaquettaire. Le CYP2C19 présente une importante variabilité interindividuelle de son activité dans la population générale due, notamment, à un fort polymorphisme génétique, avec une trentaine de variants alléliques identifiés à ce jour. Ceci résulte en cinq phénotypes distincts dans son activité : le phénotype métaboliseur lent (PM), le phénotype métaboliseur intermédiaire (IM), le phénotype métaboliseur normal (NM), le phénotype métaboliseur rapide (RM) et le phénotype métaboliseur ultra-rapide (UM).
 
Pour caractériser l'activité du CYP2C19, il existe différentes méthodes de phénotypage à savoir l'administration d'une substance-test métabolisée de manière spécifique par le CYP2C19 et la mesure de paramètres pharmacocinétiques, tels que l'aire sous la courbe (AUC), ou des ratios métaboliques entre les concentrations de la molécule-mère et de son métabolite. Les substances-tests les plus utilisées sont l'oméprazole (OPZ) et la méthénytoïne. Il est également possible de mesurer le phénotype de plusieurs isoformes des CYPs simultanément avec le phénotypage mixte, tel que le « Geneva cocktail » développé aux HUG. Ce dernier est composé de 6 substances-tests permettant de phénotyper simultanément 6 isoformes des CYPs, dont l'OPZ pour le CYP2C19.
 
Malgré une bonne tolérance de ce cocktail, certains patients peuvent être réticents à l'administration de médicaments de manière exogène et il n'est parfois pas possible de les administrer à certains patients (e.g. femmes enceintes, enfants, personnes âgées). Il convient par ailleurs d'attendre 2h après l'ingestion du « Geneva cocktail » avant d'effectuer la prise de sang, ce qui peut poser quelques contraintes pratiques en clinique.
 
L'utilisation de biomarqueurs endogènes de mesure de l'activité des CYPs permettrait ainsi de s'affranchir de ces obstacles et de rendre la pratique moins invasive et plus acceptable pour les patients. Une récente étude consacrée au CYP2D6 conduite au sein de notre service a permis d'identifier de nouveaux biomarqueurs endogènes pour cet isoforme, à savoir la solanidine, un alcaloïde aglycone très commun, et ses dérivés.
 
Le but de notre étude est d'identifier de nouveaux biomarqueurs endogènes pour mesurer (phénotyper) l'activité du CYP2C19 par métabolomique non ciblée.
 
Les volontaires sains seront stratifiés en deux groupes selon leur phénotype pour le CYP2C19 : les sujets PMs et NM-RMs-UMs. Les sujets IMs seront exclus afin d'observer des différences plus significatives au sein des deux groupes.
 
Objectif primaire :
 
 - Partie 1 : mise en évidence de potentiels substrats et/ou métabolites endogènes du CYP2C19 par métabolomique non ciblée sur des échantillons urinaires, plasmatiques et de vésicules extracellulaires dérivées du foie prélevés avant (baseline, session 1) et après administration répétée de fluvoxamine (inhibition enzymatique du CYP2C19, session 2) ainsi qu'après administration répétée de rifampicine (induction enzymatique du CYP2C19, session 3). - Partie 2 : identification des substrats et/ou métabolites endogènes du CYP2C19 parmi les composés mis en évidence dans la partie 1 par analyse semi-quantitative ciblée sur des échantillons urinaires, plasmatiques et de vésicules extracellulaires dérivées du foie des volontaires sains PMs et NM-RMs-UMs à la baseline (i.e sans administration préalable de fluvoxamine ou de rifampicine). 
Objectifs secondaires :
 
 - Identification des substrats et/ou des métabolites endogènes du CYP2C19 à l'aide de bases de données internes ou externes, par fragmentation en LC-MS/MS ou à l'aide de standards de référence. - Corrélation des concentrations plasmatiques et/ou urinaires et/ou de vésicules extracellulaires dérivées du foie d'un substrat et/ou un métabolite endogène du CYP2C19 avec le phénotype (ratio sanguin OH-oméprazole/oméprazole) et/ou le génotype du CYP2C19.

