2.9 Secondary objective

- Determination of the chemical structure of the discovered metabolites with internal or external databases, LC-MS/MS fragmentation, reference standards or NMR.
- Correlation of the relative abundance (or absolute concentration if the molecule has been identified and is commercially available) in urine and/or plasma and/or liver-derived extracellular vesicles of the discovered metabolite with the phenotype (blood $MR_{OH-OPZ/OPZ}$).
- Evaluation of the expression levels of CYP2C19 cell-free RNA (cfRNA) from extracellular vesicles and correlation with genotype, phenotype (omeprazole) and modulation of CYP2C19 activity by administration of an inhibitor (fluvoxamine) and an inducer (rifampicin).
- To compare CYP2C19 metabolomic signature of liver-derived extracellular vesicles with that of plasma and urine.
- To compare CYP2C19 metabolomic signature of liver-derived extracellular vesicles with that of total extracellular vesicles.
- Establishment of a multivariate linear regression model to predict CYP2C19 phenotype.
- Validation of the results with recombinant enzymes and human hepatocytes genotyped for CYP2C19.

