3.2 Primary and secondary endpoints

Primary endpoint:

Fold-change in the intensities of features determined by mass spectrometry according to genotype (PMs versus NMs-RMs-UMs) and according to sessions. Metabolic features showing a fold-change ≥ 1.5 or ≤ 0.67 ³⁷ will be qualified as CYP2C19 endogenous biomarkers. Chromatographic signals will be detected in healthy volunteers' urine, plasma and liver-derived

extracellular vesicles by liquid chromatography coupled to high resolution mass spectrometry (LC-HRMS) at each session for each volunteer.

Secondary endpoint:

- Correlation of significant ions measured in metabolomics with OH-OPZ/OPZ blood ratio.
- Establishment of a multivariate linear regression model to predict CYP2C19 phenotype.

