9.2 Data analysis

For metabolomics analysis, peak extraction and grouping as well as retention time correction and alignment will be performed on XCMS Online.⁸³ Then, multivariate statistical analysis as

well as univariate will be done. First of all, regarding multivariate approaches, a principal component analysis will be applied to verify the analytical variability. Partial least squares-discriminant analysis (PLS-DA), the supervised version of PCA, will also be used to maximise the separation between different groups (i.e. control session versus inhibition session versus induction session). Then, the variable importance in projection (VIP) score calculated from the PLS-DA model may be applied to identify potential biomarkers.

In univariate analysis, a volcano plot will be performed to detect any significant changes in signal intensities before and after inhibition or induction as well as between PMs and NMs-RMs-UMs. The raw p-values will be adjusted by false discovery rate method to correct for multiple testing in the first case.

All the metabolomics analysis will be performed on the online platform Metaboanalyst.⁸⁴

The possible correlation between the blood MR OH-OPZ/OPZ and significant ions identified will be evaluated using Spearman's rank correlation. Values of $p < 0.05$ will be considered significant.

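### Section 9.2 calls each ion's Spearman correlation with the omeprazole ratio significant at p < 0.05, and the stated false discovery rate adjustment does not reach these tests

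*Protocol*

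**What the plan says.** - **Test and threshold.** In section 9.2 the correlation of the significant ions with the blood OH-OPZ/OPZ ratio is to be "evaluated using Spearman's rank correlation. Values of $p < 0.05$ will be considered significant".
- **Adjustment.** The FDR sentence, earlier in section 9.2, belongs to the volcano plot: "The raw p-values will be adjusted by false discovery rate method to correct for multiple testing in the first case". The volcano plot has two uses: sessions before and after inhibition or induction, and PMs against NMs-RMs-UMs. The first case is most naturally the session comparison. On any reading the sentence precedes the correlations and does not mention them.
- **Endpoint.** Section 3.2 lists, as a secondary endpoint, "Correlation of significant ions measured in metabolomics with OH-OPZ/OPZ blood ratio". Ions are in the plural.
- **Matrices.** Section 2.9 states the objective as a correlation of relative abundance "in urine and/or plasma and/or liver-derived extracellular vesicles of the discovered metabolite with the phenotype".
- **Sessions.** Samples and the omeprazole ratio are obtained at all three sessions (section 3.1). Section 9.2 does not say which session or sessions enter the correlation.
- **Synopsis.** The French secondary objective adds a second comparator: "avec le phénotype (ratio sanguin OH-oméprazole/oméprazole) et/ou le génotype du CYP2C19". Sections 2.9, 3.2 and 9.2 give only the phenotype or the blood ratio for the metabolite correlation.

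**The concern.** The protocol recognises multiplicity elsewhere. Section 9.1 divides alpha by 5000 expected features for the sample size, and section 9.2 adjusts the volcano-plot p-values. It then attaches a plain 0.05 to a further batch of tests, whose number depends on how many ions survive discovery and in how many matrices each is examined. Followed as written, that rule will label some correlations significant by chance, and the stated 5% does not tell the reader how many to expect.

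These correlations will be read as evidence that a candidate tracks measured CYP2C19 activity, in a study whose primary objective is to identify and validate a marker. If the matrix and session are also left open, the one reported can be chosen after the results are known.

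**Working it through.** **Figures in the plan.** No error rate, power or number of tests is given for the correlation endpoint; its only figure is 0.05. The one multiplicity calculation in the protocol, in section 9.1, reproduces: 0.05 / 5000 = 0.00001, and a two-sided paired t-test with effect size 1.156 at that alpha needs n = 30 (power 0.804). That alpha was used to size the session comparison and does not carry over to the correlations.

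**Inputs.**
- Level per test: 0.05 (section 9.2), taken as two-sided because sidedness is not stated.
- Matrices: 3 (section 2.9).
- Subjects: 40, of whom 10 are PMs (section 3.1).
- Correlation of one metabolite across matrices: not in the documents; assumed 0 to 0.9.
- Number of ions: not in the documents; 10 used as an illustration.

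**One null metabolite, three matrices, one session.** With independent tests, the chance of at least one p < 0.05 is 1 − 0.95³ = 14.3%. Matrices from the same person are likely to be correlated, so null Spearman tests were simulated (n = 40, 20,000 runs per setting). Each row spans three assumed separations of the ratio between PMs and non-PMs: 0, 2 and 4 SD.

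| Assumed inter-matrix correlation | At least one p < 0.05 |
|---|---|
| 0 | 13.9–14.3% |
| 0.3 | 13.4–14.1% |
| 0.5 | 12.6–13.2% |
| 0.7 | 10.9–11.5% |
| 0.9 | 8.7–8.9% |

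The range is about 9% to 14%, or roughly 1.8 to 2.8 times the stated 5%.

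**Several ions, one test each.** For 10 independent null ions, 1 − 0.95¹⁰ = 40.1%, with 10 × 0.05 = 0.5 false calls expected. Ions that correlate with each other would give a lower chance of any false call but the same expected number.

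**What these rates leave out.** They describe an unselected null ion, whereas section 9.2 correlates only ions already found significant. In a simulation, null ions picked at unadjusted p < 0.05 on PMs against non-PMs were then correlated with the ratio in the same 40 subjects. They reached p < 0.05 in about 5% of cases when the ratio did not differ between the groups, 25% when it differed by 2 SD and 35% when it differed by 4 SD. Selection can therefore push the rate up, by a mechanism separate from the number of tests.

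**Effect of adjustment on the threshold.** With n = 40, p < 0.05 corresponds to |ρ| = t/√(38 + t²) with t = 2.024, which is 0.31. With 10 ions, the strictest step of a Benjamini–Hochberg adjustment is 0.05 / 10 = 0.005, for which t = 2.980 and |ρ| = 0.44.

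**The case against.** Several points on the other side are sound.

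- **No claim hangs on the Spearman p-value.** A reader might infer that a significant correlation declares a biomarker. The documents do not say so. Section 9.2 only calls the correlation significant. The biomarker label rests on the fold-change rule in section 3.2, with further support planned from the targeted PM comparison and from recombinant enzymes and hepatocytes. This stands, and it limits the severity.
- **Genotype should not be counted.** A reader might double the tests to six by adding genotype and arrive at a rate around 20%. Genotype appears for this correlation only in the synopsis, with no test and no alpha, and the 0.05 rule in section 9.2 names the blood ratio alone. This is a difference between synopsis and body to be reconciled, not part of the error rate.
- **Three tests per metabolite is a reading, not a statement.** The wording in section 2.9 could mean whichever matrix the metabolite was found in. The 9–14% therefore applies only if each ion is tested in all three. Multiplicity across ions remains on either reading, because the endpoint is in the plural.
- **A deciding matrix, deciding session or exploratory label may be in a statistical analysis plan that is not shown.** True, and their absence alone is not the point. The point is the threshold that section 9.2 does fix. The text does not say whether 0.05 applies to raw or adjusted values, but the only adjustment it describes is confined to the volcano plot.
- **Pre-selection might seem to protect the rule.** It does not: where the omeprazole ratio differs between the genotype groups, selecting on genotype raises the false rate.

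**Conclusion.** The concern holds in limited form. The protocol fixes 0.05 per Spearman test against the blood ratio, over several ions and possibly three matrices, and its FDR adjustment does not extend to them. Under stated assumptions, a null metabolite tested in three matrices at one session has about a 9–14% chance of at least one significant result, and ten independent null ions tested once each have about a 40% chance.

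No single rate can be derived from the documents, because the number of ions, the inter-matrix correlation and the session used are not given. These figures show the direction and order of the problem and are not the trial's operating error rate. Severity is minor to moderate: a secondary endpoint of a discovery study, with the biomarker label decided elsewhere.

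**What to change.** In section 9.2, replace the plain 0.05 sentence with a rule of this kind: Spearman p-values against the blood OH-OPZ/OPZ ratio are adjusted by the FDR method across all ions; each ion is tested in the matrix in which it was selected and at one named session (for example baseline); an adjusted p < 0.05 is called significant. Correlations in other matrices or at other sessions are descriptive and lie outside that family. Align sections 2.9 and 3.2 with this. Separately, reconcile the synopsis with sections 2.9, 3.2 and 9.2 on whether a genotype correlation is intended.

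**Cost.** Wording and one p-value adjustment, with no new data or subjects. Weak correlations lose the label significant: with 10 ions and 40 subjects the strictest step moves from |ρ| of about 0.31 to about 0.44, a modest loss for a marker meant to stand in for a probe drug.

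**Limits.** FDR controls the expected share of false calls; it holds the chance of any false call at 5% only when every ion is null. It also does not remove the bias from selecting and correlating ions in the same subjects, which should be acknowledged when the results are reported.

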9.3 Dropout and missing data management

Withdrawal volunteer will be replaced by a new volunteer. A subject screening log will be kept in the TMF and regularly updated. This document will be accessible for monitoring and inspection in order to analyze rates and reasons for non-inclusions and withdrawals.

10. ETHICAL AND REGULATORY ASPECTS

10.1 Study registration

After obtaining the agreement by the CCER and Swissmedic, this clinical trial will be registered on the international register of clinical trials (www.clinicaltrial.gov), in accordance with the requirements of the international committee of medical reviews editors. In addition, the clinical trial will also be registered in the supplementary federal database (the SNCTP).

10.2 Categorisation of study

The present clinical trial is categorised under Category B according to the OClín, art. 19. All therapeutic products are authorized in Switzerland but do not have any indication for healthy volunteers.

10.3 Ethical Committee and Regulatory Authority

The study protocol, the documents for the subjects and the investigator's list will be submitted to the CCER of Geneva canton and to the Swiss Agency for Therapeutic Products (Swissmedic). The study will only start after the formal authorisation of both the CCER and Swissmedic. During the study, the investigator and the sponsor will have the obligation to submit to the CCER and Swissmedic, respectively, the study progression, any modification to a document and any new important information about the investigational product. No changes can be made to the protocol without prior Sponsor and CCER approval, except when it is necessary to eliminate apparent immediate hazards to the study participants.

Premature study end or interruption of the study is reported within 15 days. The regular end ("last patient last visit") of the study is reported to the CCER and Swissmedic within 90 days and the final study report shall be submitted within one year after study end. Amendments are reported according to chapter 9.9.

10.4 Ethical Conduct of the Study

This study will be conducted in accordance with the ethical principles of the Declaration of Helsinki, the ICH guidelines for the Good Clinical Practices (GCP), the human research act (LRH) and the ordinance on clinical trials on research involving humans (OClin). The investigators will be responsible for the strict enforcement of the protocol during the study. The CCER and Swissmedic will receive annual safety reports and be informed about study stop/end in accordance with local requirements.

10.5 Declaration of Interest

The investigators of this clinical trial declare no conflict of interest.

10.6 Information and consent

The investigators or delegated person will explain to each participant the nature of the study, its purpose, the procedures involved, the expected duration, the potential risks and benefits and any discomfort it may entail in words easy to understand. All participants will be informed that their participation in the study is voluntary and that they may withdraw at any time without consequence or explanation. Participants must be informed that their medical records may be examined by authorized individuals other than their treating physician. All study volunteers will receive a participant information sheet and a consent form describing the study and providing

sufficient information to make an informed decision about their participation in the study. A minimum of 72 hours will be given to the volunteers to decide whether they participate or not. The volunteer's information sheet and the consent form will be submitted to the CCER to be reviewed and approved. The formal consent of a participant, using the approved consent form, must be obtained before the participant is submitted to any study procedure. The participant should read and consider all the statements before signing and dating the informed consent form, and should be given a copy of the signed document. The consent form must also be signed and dated by the investigator (or delegated person) as well as retained as part of the study records.

Participants fulfilling eligibility criteria will receive a compensation of 200 Swiss francs for each session corresponding to a total of 600 Swiss francs. Non-eligible participants will receive a compensation of 20 Swiss francs for attending the first visit.

10.7 Participant privacy and confidentiality

The investigator affirms and upholds the principle of the participant's right to privacy and that they shall comply with applicable privacy laws. Furthermore, anonymity of the participants shall be guaranteed when presenting the data at scientific meetings or publishing them in scientific journals. Individual subject medical information obtained as a result of this study is considered confidential and disclosure to third parties is prohibited. There will not be any commercial exploitation of the study subjects' medical data and biological samples.

Subject confidentiality will be further ensured through subject identification code numbers to correspond to treatment data in the computer files. For data verification purposes, authorized representatives of HUG, Swissmedic or Geneva CCER may require direct access to parts of the medical records relevant to the study, including participants' medical history.

The results obtained from genotyping and phenotyping will be communicated to the volunteers if they wish to. They will also decide in the consent form if they agree that their reversibly anonymized genetic data and biological samples (plasma and urine) will be kept for a potential further use.

Volunteers can contact the investigators at any moment if they have questions concerning the meaning of the genotyping and phenotyping results.

10.8 Early termination of the study

The Sponsor-Investigator may terminate the study prematurely according to some circumstances, for example:

- ethical concerns
- insufficient participant recruitment
- when the safety of the participants is doubtful or at risk, respectively
- alterations in accepted clinical practice that make the continuation of a clinical trial unwise
- early evidence of benefit or harm of the experimental intervention

10.9 Protocol amendments

Substantial amendments are only implemented after approval of the CCER and Swissmedic respectively. Under emergency circumstances, deviations from the protocol to protect the rights, safety and wellbeing of human subjects may proceed without prior approval of the CCER or Swissmedic. Such deviations shall be documented and reported as soon as possible to the CCER and Swissmedic. All non-substantial amendments are communicated to Swissmedic as soon as possible if applicable and to the CCER within the Annual Safety Report (ASR).

11. PUBLICATION POLICY

Data obtained from this study will be subject to publication in a peer reviewed journal.

12. FINANCING AND INSURANCE

12.1 Funds

This study is funded by the Swiss National Science Foundation (SNSF).

